6.2 Statistical analysis of efficacy and harms

6.2.1 Primary outcome analysis

For the primary analysis, the difference in the FIM-motor score (and 95%) confidence interval will be derived using unadjusted and adjusted (for important covariates) analyses, using the linear regression models. In terms of interpretation, the intervention would be said to be not unacceptably worse than (i.e., non-inferior to) the control if, when the 95% CI around the difference in the effect size between the interventions is calculated and the lower bound of the interval does not extend beyond the -2.

A further exploratory analysis to assess the impact of missing outcome data on FIM-motor score will be examined using multiple imputation techniques.

6.2.2 Secondary outcome analysis

The continuous secondary outcomes will be examined using linear regression models (with point estimated and 95% confidence intervals). Categorical outcomes will be analysed using logistic regression models (OR and 95% CI of OR).

A detailed Statistical Analysis Plan (SAP) will be written by the trial statistician and approved by the DMEC prior to any interim analysis.

6.3 Subgroup analyses

Pre-specified sub-groups will include age (<65 , ≥ 65 years old) and others which will be discussed with the Trial Steering Committee. Exploratory analyses will be reported using 99% confidence intervals. Logistic regression will be used with interaction terms (treatment group by sub-group) for the sub-

groups selected.

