2.3 Outcome measures

FIM: The primary outcome for the trial is the Functional Independence Measurement (motor) (FIM-motor). The FIM was developed as a functional assessment measure for all diagnoses in the rehabilitation setting and has been used to assess outcome in trauma populations away from the rehabilitation setting¹². The FIM consists of 18 items across 6 domains: self-care; sphincter control; mobility; locomotion; communication; and social cognition. There are 13 items related to motor activities and 5 assessing cognitive function. Each item rates the patient's level of disability on a scale from 1 to 7, with 1 representing total dependence and 7 describing complete independence without the need for an aid. Performance on each item is summed to form the FIM total score, which ranges from 18 (lowest function) to 126 (highest function). There are 2 additional sub-scores. The FIM cognitive score uses the 5 cognitive items to create a score from 5 (lowest cognitive function) to 35 (highest cognitive function). The FIM motor score sums the patient's performance on each of the motor items and ranges from 13 (lowest motor function) to 91 (highest motor function). The FIM motor score at discharge has also been found to be a significant independent predictor of return to work or study¹². Moreover, FIM motor reflects well the functional status of individuals following traumatic spinal cord injury¹³.

ASIA Impairment Scale¹⁴: The American Spinal Injury Association Impairment Scale (ASIA) is a standardized neurological examination used by the rehabilitation team to assess the sensory and

motor levels which were affected by the spinal cord injury. The scale has five classification levels, ranging from complete loss of neural function in the affected area to completely normal. Neurological deterioration is defined as the change from 'E' – normal to 'A-D' – impairment.

EQ-5D-5L¹⁵: The descriptive system comprises five dimensions: mobility, self-care, usual activities, pain/discomfort and anxiety/depression. Each dimension has 5 levels: no problems, slight problems, moderate problems, severe problems and extreme problems. The patient is asked to indicate his/her health state by ticking the box next to the most appropriate statement in each of the five dimensions.

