2.3.1 Effectiveness

Primary effectiveness outcome:

- Total Functional Independence Measurement motor (FIM-motor) score at discharge. The FIM is an 18-item instrument measuring a person's level of disability in terms of burden of care. The FIM should be rated by the consensus opinion of a multidisciplinary team, but the evaluation is often performed by a single professional.

Secondary effectiveness outcomes:

- FIM-motor at 30 days, 180 days after randomisation at video clinic or follow up appointment;
- FIM-total and cognition scales at discharge, 30 days and 180-day at video clinic or follow up appointment;
- ASIA Impairment Scale at discharge;
- Mortality (at days 30, 90 and 180);
- Intervention for c-spine injury in the first 30 days or discharge (use of collar for > 2 weeks, halo brace, c-spine surgery);
- Discharge destination;
- Pre-hospital analgesic requirements (from Ambulance PRF).

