6. STATISTICAL ANALYSIS

6.1 Power and sample size

The planned size of this trial is 8316 patients (4158 per arm). The sample size is based on a non-inferiority hypothesis, where our objectives are to demonstrate that the movement minimisation (intervention) is no worse than triple immobilisation (comparator), by a pre-specified small difference, δ , on the functional outcome (FIM-motor) score. Statistically, our null hypothesis is that the intervention is inferior to the comparator by δ , and the alternative is that the intervention is non-inferior to the comparator by amount δ . Choosing δ as 2 points on the FIM-motor, as the difference that is clinically acceptable as a margin of non-inferiority between the interventions, then using a standard deviation of 25.93, 90% power and two-sided 5% significance level (with loss-to-follow-up rate of 15%), we would require a total sample of 8316 patients. The sample size was informed using the following parameters:

1. Non-inferiority margin: Regulatory guidelines recommend defining the margin based on a review of historical evidence of the efficacy of the comparator^{19,20}. The minimal clinically important difference (MCID) for the FIM-motor is not established for the spinal cord injury patients²¹. However, using data from acute stroke patients, the MCID = 22 points (for FIM total), 17 points (for FIM-motor) and 3 points (for FIM-cognition) subscale²². This would suggest that a MCID for the FIM-motor (over the total or subscale scores) can be taken to be at least 3 points. Thus a 2-point difference on the FIM-motor scale, can be considered as a

viable non-inferiority margin. This equates to an effect size of 0.1, which using Cohen's criteria²³ would be below what is classed as a 'small' effect size usually specified for superiority studies.

2. Type 1 error: Using regulatory guidance from the EMA CHMP26 we specify a two-sided 0.05 level of significance (or one-sided 0.025). An alternative way of stating this requirement is that the lower bound of the two-sided 95% confidence interval (or one-sided 97.5% interval) for the difference between active and placebo should be above zero.

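### The only subgroup model named, logistic regression, does not suit the continuous primary outcome, and no outcome is specified for it

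*Protocol*

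**What the plan says.** - **Primary outcome.** Section 2.3.1 gives it as "Total Functional Independence Measurement motor (FIM-motor) score at discharge". Section 2.3 says that this score "ranges from 13 (lowest motor function) to 91 (highest motor function").
- **Primary analysis.** Section 6.2.1 derives the difference in scores "using unadjusted and adjusted (for important covariates) analyses, using the linear regression models". Non-inferiority is concluded if "the lower bound of the interval does not extend beyond the -2".
- **Margin and sample size.** Section 6.1 sets the margin in points ("Choosing δ as 2 points on the FIM-motor, as the difference that is clinically acceptable as a margin of non-inferiority") and sizes the trial "using a standard deviation of 25.93, 90% power and two-sided 5% significance level (with loss-to-follow-up rate of 15"%).
- **Secondary outcomes.** Section 6.2.2 matches the model to the outcome type: linear regression for continuous outcomes, logistic regression with odds ratios for categorical ones.
- **Subgroups.** Section 6.3 names age (under 65, and 65 or over), leaves further factors to the Trial Steering Committee, and reports exploratory analyses with 99% confidence intervals. Its only statement on the model is "Logistic regression will be used with interaction terms (treatment group by sub-group"). It does not say which outcome is meant.

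**The concern.** Logistic regression needs a binary outcome, or a categorical one in its extended forms. FIM-motor is neither as the protocol defines it, and no responder definition or threshold is given. The sentence in section 6.3 therefore provides no usable model for the outcome on which the trial will be judged. It also drops the distinction between continuous and categorical outcomes that section 6.2.2 makes just before it.

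At stake is whether the effect of movement minimisation on FIM-motor can be compared between younger and older patients in the units of the primary result. Age matters in this population: section 1.1 reports a median age of 59 years in the trauma registry and says that cord contusion without fracture is more common in older people. A ratio of odds ratios between age groups cannot be placed beside a mean difference in points or beside the margin of -2.

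This is more than detail left to the SAP, because the protocol states a model. A SAP that follows section 6.3 must invent a cut-off if it is to cover FIM-motor, and a SAP that uses linear regression departs from the protocol.

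**Working it through.** **1. Is the design on the point scale?** Inputs from section 6.1: margin 2, SD 25.93, power 90%, one-sided 2.5%, loss 15%. The assumed true difference is zero.

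n per arm = 2 × (1.960 + 1.282)² × 25.93² / 2² = 3,533 after rounding up, or 7,066 in total.

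Allowing for loss: 3,533 / 0.85 = 4,157 per arm (8,314 in total), or 7,066 / 0.85 = 8,313. The protocol states 8,316, so its figure is reproduced to within rounding. The trial is sized on a difference in mean score, not on a proportion.

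**2. Sections side by side.**

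| Section | Outcome | Model | Scale of result |
|---|---|---|---|
| 6.2.1 | FIM-motor at discharge | linear | points, against -2 |
| 6.2.2 | continuous secondary | linear | mean difference |
| 6.2.2 | categorical secondary | logistic | odds ratio |
| 6.3 | not named | logistic with interaction | odds ratio, ratio of odds ratios |

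Only the last row gives a model without tying it to an outcome type.

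**3. Can the margin be carried over to an odds ratio?** Only with a cut-off and a distribution. As an illustration, assume a normal score with mean 61 (section 6.1 gives 61 as a median) and SD 25.93, and lower the mean by 2 points:

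| Cut-off | Proportion above, mean 61 | Proportion above, mean 59 | Odds ratio |
|---|---|---|---|
| 40 | 0.791 | 0.768 | 0.875 |
| 60 | 0.515 | 0.485 | 0.884 |
| 70 | 0.364 | 0.336 | 0.882 |
| 80 | 0.232 | 0.209 | 0.875 |

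The values lie close together under this assumption. The protocol, however, supplies neither the cut-off nor the distribution, so it gives no odds ratio that corresponds to -2 points.

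**4. What would a linear interaction model deliver?** Evaluable patients: 8,316 × 0.85 = 7,069, or about 3,534 per arm. Assume SD 25.93 in both age groups and no gain from covariates. The protocol does not give the age split, so two are shown. With n per arm in a subgroup, the 99% half-width is 2.576 × 25.93 × √(2/n). The half-width for the interaction is the square root of the sum of the two squared half-widths.

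| Age split | n per arm in each group | 99% half-width in each group | 99% half-width, interaction |
|---|---|---|---|
| 50/50 | 1,767 and 1,767 | 2.25 and 2.25 | 3.18 |
| 30/70 | 1,060 and 2,474 | 2.90 and 1.90 | 3.47 |

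For a half-width of 2 points, a subgroup needs n = 2 × (2.576 × 25.93 / 2)², or about 2,230 per arm. That is 2,230 / 3,534 = 63% of evaluable patients.

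**The case against.** The strongest reply is that section 6.3 names no outcome. The protocol has outcomes for which its sentence is valid as it stands: mortality at 30, 90 and 180 days, further intervention for c-spine injury, and neurological deterioration defined as a change from normal to impaired. A reader might infer that the protocol prescribes logistic regression for FIM-motor; it does not say so. This part of the objection stands. But if the sentence is meant only for binary outcomes, it lacks the restriction that section 6.2.2 makes, and the protocol then has no subgroup model for its primary outcome. The mismatch remains on either reading.

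Three stronger inferences are not supported:

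- **That a cut-off would be picked after the data are seen.** Section 6.2.2 requires a detailed SAP approved before any interim analysis. That SAP is not at hand, and it may fix a threshold or use a linear model. A drafting slip is a plausible explanation.
- **That a known share of information would be lost.** The textbook loss from a median split assumes a roughly normal score. The protocol plans no median split. Section 1.1 says that injury is ruled out in the emergency department in most immobilised patients, and section 3.2.2 records those who leave before data collection as totally independent. A pile-up at the top of the scale is therefore plausible, and the textbook figure would not apply.
- **That a linear model would settle non-inferiority in older patients.** An interaction test addresses heterogeneity, not whether the effect in one group stays above -2. The protocol makes no claim of non-inferiority by subgroup, and at a 50/50 split the intervals would be wider than the margin.

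**Conclusion.** The point holds in a limited form. Section 6.3 states a single subgroup model that does not suit the continuous primary outcome, names no outcome, and departs from the protocol's own division between linear and logistic regression. With no FIM-motor cut-off defined, following the section literally either omits the primary outcome or calls for an undefined dichotomy, with results off the point scale.

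The consequence is modest. The primary test, the margin and the sample size are unaffected, and the subgroup results stay exploratory after correction. The precision figures rest on the assumptions in step 4 of the working. The mismatch itself rests on the text alone and needs none of them.

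**What to change.** Replace the sentence on the model in section 6.3 with:

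*For FIM-motor and other continuous outcomes, linear regression with a treatment-by-subgroup interaction will be used, reporting the mean difference with 99% CI in each subgroup and for the interaction, with the same covariates as the primary model. Logistic regression will be used only for binary outcomes.*

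This names the outcomes, brings section 6.3 into line with sections 6.2.1 and 6.2.2, and puts the subgroup results in the same units as the primary result. If a SAP exists, check that it says the same. The cost is one sentence, with no change to sample size or data collection.

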6.4 Interim analysis and criteria for the premature termination of the trial

The timing and frequency of the interim analyses will be discussed and agreed with the Data Monitoring Committee members. It is anticipated that no more than one formal interim analysis will take place during the course of the study. The statistical stopping criteria will be formalised using the O'Brien and Fleming stopping rules²⁷. In making a decision to terminate the clinical trial, the Data Monitoring Committee will use the statistical evidence as guidance to their decision making and will be also presented with a 95% confidence interval of the treatment difference.

6.5 Health Economic Evaluation

A prospectively planned economic evaluation will be conducted from an NHS and personal social services perspective, in accordance with an agreed Health Economics Analysis plan (HEAP). The methods will adhere to the recommendations of the NICE Reference Case²⁸.

Resource use will include intervention, hospital (ICU, HDU and ward days) and community costs (primary care and social care costs) in the 6 months following intervention. Resources will be costed using national reference unit costs where available, reflatd to current prices.

Health-related quality of life (EQ-5D-5L/EQ-5D-Y) responses will be used to generate quality-adjusted life years (QALYs) using the value set recommended by NICE at the time of analysis²⁹ and area-under-the curve (AUC) method. The baseline EQ-5D-5L/EQ-5D-Y values will be imputed to reflect the unconscious health state and applied to all patients, minimising potential bias in the QALY AUC calculation³⁶. Within-trial analysis (to 6 months) using bivariate regression of costs and QALYs will inform a probabilistic assessment of incremental treatment cost-effectiveness. Following best practice, missingness mechanisms will be explored, and multiple imputation methods will be used where appropriate to avoid biases associated with complete case analysis. Costs and outcomes arising during the trial will be undiscounted, reflecting the 6-month time horizon. Sensitivity analyses will be undertaken to explore uncertainty in the incremental cost-effectiveness and to consider issues of generalisability of the study.

Although not anticipated to be necessary, more extensive economic modelling using decision-analytic methods may be considered to extend the time horizon and decision context if costs and benefit profiles are non-convergent or non-dominant at 6 months. Such modelling will draw upon best available information from the literature and stakeholder consultations to supplement the trial data. Parameter uncertainty in the decision-analytic model will be explored using probabilistic sensitivity analysis. Longer term costs and consequences will be discounted to present values using discount rates recommended for health technology appraisal in the UK (current discount rate: 3.5%)

7. TRIAL ORGANISATION AND OVERSIGHT

7.1 Sponsor and governance arrangements

Imperial College London will act as the Sponsor for the trial. All trial-related activity will be undertaken according to the principles set out in the Good Clinical Practice Guidance and in accordance with the UK Policy for Health and Social Care Research.

7.2 Ethical approval

Ethics committee review of the trial protocol and documents essential to the trial will be carried out by a UK NHS research ethics committee, flagged for studies involving adults lacking capacity. HRA approval will be obtained before the trial starts. Before enrolling patients into the trial, each trial site must ensure that the local conduct of the trial has been reviewed by the relevant NHS Trust Research & Development (R&D) department.

Sites will not be permitted to enrol patients into the trial until written confirmation of the approval via the HRA and the confirmation of capacity and capability for the relevant participating Trust is received by the SIS trial team, based at WCTU.

Annual reports will be submitted to the REC within 30 days of the anniversary date on which the favourable opinion was given, and annually until the trial is declared ended. The REC and HRA will be notified of any amendments, and once the trial concludes a final report will be provided in accordance with reporting requirements. In accordance with Warwick SOPs, the CI is responsible for making applications to the relevant authorities if an amendment to the research protocol or other trial document or process is required. The CI may designate a member of staff to prepare the amendment submission but retains responsibility for any amendment application, however, the CI is no longer required to sign the completed amendment tool but should be copied into any correspondence with the relevant sponsors' office. It is the sponsor's responsibility to assess whether an amendment is to be regarded as 'substantial' on a case-by-case basis and confirm their opinion with the CI or their delegate prior to any application being made. The sponsor is required to review and sign off the amendment tool prior to locking for submission. This will be returned to WCTU for submission and processing of the amendment. The WCTU trial management team will ensure that an impact assessment is carried out on all key trial documents (e.g. protocol, CRFs, data management plan, SAP, Risk Assessment and Monitoring Plan) to check if any associated documents require amending based on the proposed amendments to the trial.

As part of the funding decision by the NIHR HTA, the trial has been reviewed by both the HTA board and independent individuals with clinical, methodological, and patient involvement expertise. It is a requirement to send to the NIHR any protocol amendment documents for their approval prior to submission to the main REC.

7.3 Trial Registration

The SIS trial has been registered with the International Standard Registered Clinical Trial Number (ISCTRN) registry.

7.4 Notification of serious breaches to GCP and/or trial protocol

Deviations from the clinical trial protocol and GCP can occur. The majority of these instances are technical deviations that do not result in harm to the trial subjects or significantly affect the scientific value of the reported results of the trial. A violation is a failure to comply with or variance from GCP and/or the final approved protocol. This results from error, fraud or misconduct. These cases should be documented in the protocol non-compliance form for the trial and appropriate corrective and

Page 37 of 42

preventative actions taken. Deviations and violations will be included and considered when the clinical trial report is produced, as they may have an impact on the analysis of the data.

A “serious breach” is a breach which is likely to effect to a significant degree –

- (a) the safety or physical or mental integrity of the subjects of the trial; or
- (b) the scientific value of the trial

The sponsor will be notified immediately of any case where the above definition applies during the trial conduct phase.

The sponsor of a clinical trial will notify the licensing authority in writing of any serious breach of

- (a) the conditions and principles of GCP in connection with that trial; or
- (b) the protocol relating to that trial, as amended from time to time, within 7 days of becoming aware of that breach

7.5 Indemnity

Imperial College London holds negligent harm and non-negligent harm insurance policies which apply to this trial.

7.6 Trial timetable and milestones

Month	Year 1				Year 2				Year 3					
	1	4	7	10	13	16	19	22	25	28	31	34	37	40
Trial Set up														
Pilot recruitment														
VOI Analysis														
Main recruitment														
Follow up														
Analysis and reporting														

7.7 Administration

The trial co-ordination will be based at Warwick Clinical Trials Unit, Warwick Medical School, University of Warwick. WCTU has expertise in undertaking studies in emergency and critical care. The trial will be run to WCTU SOPs.

The WCTU will be responsible for protocol development, ethics and governance approvals, database development and data management, randomisation, trial management and monitoring, analysis of the data and reporting.

7.8 Trial Management Group (TMG)

The Trial Management Group, consisting of the project staff and co-investigators involved in the day-to-day running of the trial, will meet regularly throughout the project. Significant issues arising from management meetings will be referred to the Trial Steering Committee or Investigators, as appropriate.

7.9 Trial Steering Committee (TSC)

The trial will be guided by a group of respected and experienced personnel and trialists as well as at least one PPI representative. The TSC will have an independent Chairperson. Face to face meetings

will be held at regular intervals determined by need but not less than once a year. Routine business is conducted by email, post or teleconferencing.

The Steering Committee, in the development of this protocol and throughout the trial will take responsibility for:

- Major decisions such as a need to change the protocol for any reason
- Monitoring and supervising the progress of the trial
- Reviewing relevant information from other sources
- Considering recommendations from the DMC
- Informing and advising on all aspects of the trial

The full remit and responsibilities of the TSC will be documented in the Committee Charter which will be signed by all members.

